Date: 11/02/21

Title: Mechanisms of Refractory Hypertension (Reserpine)

NCT Number: NCT03223272

Date of Last Protocol Approval: 06/09/21

PI: [name]
University of Alabama at Birmingham
Birmingham, AL 35294

Study Protocol

1. Study Title: Mechanisms of Refractory Hypertension (Reserpine)
2. Hypothesis: Reserpine, a potent sympatholytic agent will substantially reduce blood pressure (BP) in patients with refractory hypertension.
3. Inclusion Criteria: Patients (age 19-80 years) referred to UAB Hypertension Clinic with refractory hypertension defined as uncontrolled office BP adherent with 5 or more antihypertensive agents, including a long-acting thiazide diuretic and spironolactone.
4. Exclusion Criteria: chronic kidney disease (eGFR <30 ml/min/1.73 mm), pregnancy
4. Primary Endpoint: Change in 24-hr ambulatory systolic BP
5. Study design: Subjects will be withdrawn from centrally-acting alpha-1 agonists agents (i.e., clonidine, guanfacine) over a 1-2-week period, if appropriate. A baseline 24-hr ambulatory BP monitoring will be done with subjects taking all of their normally prescribed antihypertensive agents. Subjects will then be dispensed reserpine 0.1 mg in open-label fashion to be taken daily for 4-weeks. At the end of the 4-week treatment period the 24-hr ambulatory monitoring will be repeated.
6. Statistical Plan: The protocol will be done as a proof-of-concept. Values will be presented as mean+/-standard deviation. Change in 24-hr ambulatory systolic BP from baseline to end-of-treatment will be compared by paired T-test.
7. Publication Plan: Study results will be presented at national hypertension meetings and submitted to a peer-reviewed medical journal for consideration of publication.

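### Blood pressure still changing after withdrawal of a central agent cannot be separated from the reserpine effect, because the baseline interval is unstated and withdrawn and non-withdrawn subjects are pooled

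*Combined protocol and SAP*

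**What the plan says.** Section 5 (Study design) sets out four steps in order:

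1. Withdrawal of central agents, for some subjects: "Subjects will be withdrawn from centrally-acting alpha-1 agonists agents (i.e., clonidine, guanfacine) over a 1-2-week period, if appropriate".
2. One baseline recording: "A baseline 24-hr ambulatory BP monitoring will be done with subjects taking all of their normally prescribed antihypertensive agents".
3. Treatment of everyone: "Subjects will then be dispensed reserpine 0.1 mg in open-label fashion to be taken daily for 4-weeks".
4. One follow-up recording: "At the end of the 4-week treatment period the 24-hr ambulatory monitoring will be repeated".

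No recording before the withdrawal is described, and no control arm. The section does not state the interval between the last dose of the withdrawn agent and the baseline recording.

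Section 6 (Statistical Plan) gives one analysis: "Change in 24-hr ambulatory systolic BP from baseline to end-of-treatment will be compared by paired T-test". It does not distinguish subjects by withdrawal status. It states no sample size, SD, target effect or significance level, and describes the study in these terms: "The protocol will be done as a proof-of-concept".

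The hypothesis in Section 2 is causal: "Reserpine, a potent sympatholytic agent will substantially reduce blood pressure (BP) in patients with refractory hypertension".

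**The concern.** In an uncontrolled before-after study the baseline is the only comparator. Here the protocol itself may disturb that comparator in some subjects, by stopping an antihypertensive in the weeks before it is measured. Subjects who never took a central agent are not disturbed in this way. If blood pressure in withdrawn subjects is still moving when the baseline is taken, that movement enters the primary endpoint. The pooled t-test would assign it to reserpine, and no planned analysis would show that this had happened.

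The baseline sentence adds a second difficulty. It has subjects on their full usual regimen, while the preceding sentence has some of them taken off part of it. For a withdrawn subject, the text does not settle whether the central agent is on board at baseline, and the possible direction of bias depends on the answer.

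**Working it through.** **Inputs.** The order of events and the single paired test come from Sections 5 and 6. There is no planned figure to reproduce. Share withdrawn, size of any rise, SD of change, sample size and a two-sided 0.05 level are all assumptions.

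**Model.** Let W be the effect of having stopped the central agent on a withdrawn subject's blood pressure at a given recording. Then:

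- change in a withdrawn subject = reserpine effect + (W at week 4 − W at baseline)
- bias in the pooled mean = share withdrawn × (W at week 4 − W at baseline)

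**Direction of the bias in four cases.**

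- *Settled effect.* W is +15 mmHg at both recordings: 15 − 15 = 0, so there is no bias.
- *Rebound that resolves.* W is positive at baseline and zero at week 4. The bias is negative and favours reserpine.
- *Residual drug effect at baseline that then wears off.* A further rise of 5-10 mmHg by week 4, with 10-50% withdrawn, gives 0.10 × 5 = +0.5 up to 0.50 × 10 = +5 mmHg, against reserpine.
- *Central agent still on board at baseline and stopped afterwards* (one reading of the baseline sentence). A sustained rise of 5-20 mmHg gives 0.10 × 5 = +0.5 up to 0.50 × 20 = +10 mmHg, against reserpine.

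**Mean bias for a fully resolving rebound (mmHg) = −share × rise.**

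| Share withdrawn | Rise 5 | Rise 10 | Rise 20 |
|---|---|---|---|
| 10% | −0.5 | −1.0 | −2.0 |
| 25% | −1.25 | −2.5 | −5.0 |
| 50% | −2.5 | −5.0 | −10.0 |

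**Chance of a significant fall when reserpine does nothing.** Simulated paired t-test, 20,000 runs per cell, n = 20, SD of change 10 mmHg within each group of subjects; nominal rate in this direction 2.5%.

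| Share withdrawn | No rise | Rise 5 | Rise 10 | Rise 20 |
|---|---|---|---|---|
| 10% (2 of 20) | 0.026 | 0.041 | 0.052 | 0.074 |
| 25% (5 of 20) | 0.024 | 0.071 | 0.137 | 0.311 |
| 50% (10 of 20) | 0.024 | 0.171 | 0.464 | 0.915 |

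*Hand check of one cell (50%, rise 10).* The mean shift is −5. The pooled SD is about √(10² + 0.5 × 0.5 × 10²) = √125 = 11.2, so the standard error is 11.2/√20 = 2.5 and the expected t is about −2.0. The critical value on 19 degrees of freedom is 2.09, so rejection in a little under half of trials is what one expects.

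**Dependence on the other assumptions** (rises of 5, 10 and 20 mmHg).

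- SD 15, n = 20: 0.054, 0.089, 0.194 at 25% withdrawn; 0.105, 0.254, 0.672 at 50%.
- SD 10, 50% withdrawn: 0.092, 0.216, 0.479 at n = 10; 0.313, 0.807, 0.999 at n = 40. A larger trial makes a false positive more likely, because the bias does not shrink with n.

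In non-withdrawn subjects analysed alone, the rate stays at 0.023-0.026 whatever the rise.

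**The case against.** The strongest defence is that withdrawing first and measuring baseline second is what keeps the background regimen the same at both recordings. That is right as far as it goes, and it disposes of several stronger readings.

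- *A reader might infer that the whole effect of stopping the central agent is credited to reserpine.* It is not. If baseline follows withdrawal, a stable effect is in both recordings and cancels.
- *A reader might infer that withdrawn subjects show reserpine in place of the central agent.* That contrast would need a recording before withdrawal, and none is described. If both recordings are off the agent, the change is reserpine added to the remaining regimen.
- *A reader might infer that the plan has no settling interval.* The text is silent on the interval, which is not the same as stating there is none. The withdrawal is also gradual and conditional, so a rebound is possible but not established. Silence still allows a baseline immediately after the last dose.
- *A reader might infer that the bias always flatters reserpine.* That is true only of a rise that resolves. Residual drug effect, or a baseline taken on the agent, works the other way.
- *A reader might infer that efficacy should be read only from non-withdrawn subjects.* They are a non-randomised subgroup of unknown and perhaps very small size. Their change is also uncontrolled, so it removes this one bias without isolating a reserpine effect.

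The numbers rest wholly on assumption, and the share withdrawn could be nil. What stands is that the plan, followed exactly, could not detect drift after withdrawal. Proof-of-concept status does not remove that difficulty, since the concept to be proved is that reserpine lowers the pressure.

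**Conclusion.** The concern holds in a limited form. The interval since the last central-agent dose is unspecified, the drug state at baseline is ambiguous, and one uncontrolled test pools two kinds of subject. Any blood pressure change in progress between the recordings is therefore confounded with reserpine, in either direction.

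The size cannot be determined from the documents. With few withdrawn subjects the effect on the error rate is small; with half withdrawn and a large resolving rebound, a significant fall would be near certain under no drug effect. Both figures assume n = 20, an SD of 10 mmHg and a rise that has gone completely by week 4. They show how sensitive the design is and do not predict this trial's result. The point is worth correcting because the plan anticipates such subjects and the correction is cheap.

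**What to change.** Leave the withdrawal procedure as it is, and make these changes to the documents:

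1. **Section 5.** Reconcile the withdrawal and baseline sentences, so that it is clear whether a withdrawn subject is on or off the central agent at the baseline recording. Record withdrawal status, the date of the last dose, and the days from that date to the baseline recording.
2. **Section 6.** Keep the all-subjects paired change as the primary analysis. Prespecify the same paired change separately for withdrawn and non-withdrawn subjects, each with n, mean, SD and confidence interval. Designate the non-withdrawn subjects as a sensitivity analysis. List the days to baseline for each withdrawn subject.
3. **Interpretation.** State in advance that if the fall is not similar in the non-withdrawn subjects, the pooled fall will not be attributed to reserpine alone. Judge similarity on the estimates and their intervals, since a small subgroup may miss significance for want of numbers. Do not describe the withdrawn group as reserpine replacing the central agent.

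The cost is a few lines of text and one recorded date, with no extra visit, procedure or patient. The downside is that the subgroup estimates will be less precise than the pooled one and may look less favourable.
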